6.3 PATIENT SETS ANALYSED

Four patient sets are defined: "all enrolled", "all eligible" and "restricted" and "matched"; the following rules are used to assess if a patient is included in an analysis set:

ENROLLED: if patient is entered in EDC system and Informed Consent is signed.

ELIGIBLE: if patient is ENROLLED and is eligible (see [Table 6.2: 1](#)). For all sites, all attempts to obtain approval for all visit forms up to final database lock or to site closure for closed sites are made. In addition, for the final database lock, patients not fulfilling the below additional criteria (previously used for Phase II outcome analyses) will be excluded from the final analyses:

For patients from open sites

- Medications form is approved (i.e. signature is available)
- All other available forms are marked as complete (unless there are forms that contain no data i.e. 'blanked forms' due to entry errors)

For patients from closed sites

- Medications form is marked as complete
- All other available forms are marked as complete (unless there are forms that contain no data i.e. 'blanked forms' due to entry errors)

Excluding patients not fulfilling the additional criteria above may generate selection bias if the excluded eligible patients differ in terms of exposure to index antithrombotic treatment or in terms of outcomes. In addition, it may make the results less generalizable if the excluded patients differ in their baseline characteristics from the other eligible patients. To assess these risks, the following analyses will be performed:

- The proportion of patients with any outcome of interest will be compared between eligible patients not fulfilling the additional criteria and the ones fulfilling them
- The index antithrombotic treatment prescribed will be compared between those groups
- If the eligible patients not fulfilling the data cleaning criterion are ≥ 100 , a description of their baseline characteristics will be done

Depending on the results of these assessments, sensitivity analyses with different definitions of the additional eligibility criteria may be performed. The outputs for these sensitivity analyses may be reported along with the main analysis results.

Sensitivity analyses using alternative criteria definitions may include:

- 1) First sensitivity analysis (more restrictive eligibility criteria)
 - For patients from open sites, all available forms should be approved where applicable (i.e. signature is available) (unless there are forms that contain no data i.e. 'blanked forms' due to entry errors)
 - For patients from closed sites, the criteria remain unchanged.

The purpose of this definition is to focus on the data with the higher quality level.

- 2) Second sensitivity analysis (no additional eligibility criteria)

No additional eligibility criteria on top of those specified in [Table 6.2: 1](#) would be considered in this sensitivity analysis. All patients who fulfil the criteria in Table 6.2:1 would be included for analyses.

RESTRICTED: The restricted population is composed of all eligible (defined by [Table 6.2: 1](#) and above additional criteria) patients within the trimmed patient set which lie within the region of propensity score overlap (for definition see [Section 7](#)). As the propensity score analysis will be based on eligible patients who at least once took the prescribed treatment, the restricted population excludes patients prescribed the treatment but who did not take it.

The restricted patient set is defined for Dabi and VKA patients only. Only Dabi and VKA patients are shown to be comparable in Phase II and their comparison is the main focus in Phase III. If later on BI considers performing other treatment group comparisons a similar approach and a similar patient set definition might be used for other treatment groups.

MATCHED: The patient set used for PS matched pair analysis (for a detailed definition see [Section 7.6](#) sensitivity analyses).

For the 1160.129 study report, patient sets are derived based on all patients enrolled globally whereas for the 1160.136 study report, patient sets are restricted to patients enrolled in the EU/EEA member states and Switzerland.

6.5 POOLING OF CENTRES

Not applicable.

6.6 HANDLING OF MISSING DATA AND OUTLIERS

In general missing data will be handled by imputation. If cause of death is missing (neither provided on the patient vital status page nor on the outcome events page) the death will be considered as "death of unknown cause" during the data collection. If a reason of death is not

entered on the outcome CRF page but only in the free text field on the vital status page (vital status page is only to be filled for patients who discontinued the study early but allowed for vital status follow up), a medical review will be done to classify the death into vascular/non-vascular/unknown death. The classification will be documented prior to final database lock in the report planning meeting/database lock meeting minutes. For the outcome analyses regarding vascular death, as the primary approach, multiple imputation will be used to impute the unknown cause of death using the data of patients who died. The following further two alternative approaches will be considered as sensitivity analyses: (1) Unknown cause of death will be imputed as a vascular cause; (2) Unknown cause of death will be imputed as a non-vascular cause. As an additional optional sensitivity analysis for the composite outcomes, all cause death would replace vascular death ([Section 7.6](#)).

Incomplete/Missing information on outcome event occurrence / medication due to changes in visit schedule

Missed visits and visits outside visit schedule (see protocol): The CRF is set up in such a way that investigators have to enter all outcome event information and changes in medication since the last study visit; therefore complete information on outcome events is ensured even if intermittent visits are missed by using all available information from the completed study visits.

Missing outcome event date information:

The handling of missing outcome event date will be handled on a patient by patient basis. If the outcome event date for a patient is missing, all collected data for this patient will be reviewed to recover the missing outcome event date. If no information is available, the date of the outcome event will be imputed with the start of the initial treatment regimen episode+1day, if the event was documented in the first follow up visit; and with the visit date of the previous follow up visit, otherwise. The proportion of patients with partial dates will be evaluated.

The decision for each missing date will be documented in the report planning meeting minutes.

Other missing dates:

Missing or incomplete AE dates are imputed according to BI standards (see DM&SM “Handling of missing data and incomplete AE dates” [\[4\]](#)). Other special handling for missing dates will be documented in the report planning meeting.

Missing baseline data in context of multivariable modelling

See [Section 7.6](#).

Patients discontinued prematurely from study

In order to assess the effects of lost to follow-up patients, percentages of dropouts and reason for loss to follow-up will be summarized in patients with a pre-planned follow up (all patients in Phase III). In addition, baseline characteristics of patients (including treatment) will be compared over all treatment groups (full cohort, eligible patient set) between:

- Patients who were lost to follow-up
- patients with a complete follow-up
- patients who discontinue early for other reasons,

Only categories with at least 100 patients will be considered for the comparison. If the number of patients lost to follow-up is below 100, this group will not be characterized separately but pooled with patients discontinued early for other reasons.

Outliers

No specific analysis regarding to outliers is planned.

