5. OUTCOMES

5.1 MAIN OUTCOMES

The objectives of the study are

a) To investigate the patient characteristics influencing the choice of antithrombotic treatment for the prevention of stroke in non-valvular atrial fibrillation (AF) patients.

In order to address objective a), the same variables (demographic and lifestyle factors, disease characteristics, antithrombotic treatment characteristics and other chronic concomitant medication) will be defined and classified as for the Phase II interim study report for 1160.129 (c02207362-02) [\[3\]](#). Antithrombotic treatment groups are defined in [Section 6.1](#).

b) To collect real world data on important outcome events of antithrombotic treatments for the prevention of stroke.

The following events were considered in the 1160.129 protocol as “important outcome events”:

- Stroke (hemorrhagic and ischemic, uncertain classification)
- Transient ischemic attack (TIA)
- Systemic embolism (SEE)
- Pulmonary embolism
- Myocardial infarction (MI)
- Major bleeding events (including life-threatening bleeding events; see definition in study protocol) (MBE)
- Life-threatening bleeding events (see definition in study protocol; derived from bleeding page except for fatal bleeds which are derived as all MBEs which are linked to an SAE with “outcome= fatal” and/or “seriousness code=fatal”).
- All cause death
- Vascular death

In addition, the following two composite outcomes, also defined in the 1160.129 protocol, will be analyzed:

- Stroke, systemic embolism, myocardial infarction, life-threatening bleeding events and vascular death
- Stroke, systemic embolism, myocardial infarction and vascular death (vascular composite outcome)

The outcome event analysis will primarily be based on the data collected on the outcome CRFs (event (yes/no) and date of occurrence). The only exceptions will be made for patients who died, i.e. patients with:

- fatal AEs and without the death being documented on the outcome CRF; the death will be considered in the outcome analysis with “date of death= end date of AE”.
- “vital status=dead” and without the death being documented on the outcome CRF or on an AE form; the date of death from the vital status page will be used.

During the data cleaning process, adverse events potentially indicating an outcome event with no matching entry on the outcome CRFs will be queried.

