6.8 CALCULATION OF TIME TO EVENTS OR CENSORING

The derivations of time to event and time to censoring for the time to event analyses are specified in this section. The information from the outcome event pages will be used to collect events. Deaths reported via the vital status or serious adverse event page will also be included.

Events to be counted in the study period are all events with onset date \leq patient’s study termination date. Events occurring after the patient’s study termination date will NOT be included in the analysis (irrespective of whether they occur during the washout period or later) as treatment information will in general not be documented in the CRF for this time period. The event death is an exception. Death captured via the vital status page will still be considered after the patient’s discontinuation.

For composite outcome events, the onset date of the first occurring component event will be used.

The following rules will be used for the main analysis of outcome events:

The analysis will be based on the antithrombotic treatment choice selected at baseline (long-term treatment information, as collected in the following CRF question: “Please report any antithrombotic treatments that you prescribed for long term use at the time of the baseline visit, or any antithrombotic treatments that the patient was already on at the time of the baseline visit that the patient will remain on for long term use”) and the initial treatment regimen episode (as specified in [Section 6.1.2](#)). An event will be counted for the main analysis if it occurs during the initial treatment regimen episode of the antithrombotic therapy selected at baseline.

The time to event will be calculated as: event date - initial treatment regimen episode start date + 1.

The time to censoring will be calculated as initial treatment regimen episode stop date - initial treatment regimen episode start date + 1 (as described in [Table 6.1.2:1](#)).

Patients participating in a clinical trial with a drug or device or in another international drug study or registry on the use of oral anticoagulation in AF will be censored when they enter the trial/study. The exception is with clinical studies of idarucizumab (Praxbind) where explicit provision for collection of this data has now been included.

The following rules will be used for the intention-to-treat analysis of outcome events :

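### Deaths known only from a fatal AE/SAE form have their vascular status imputed even when that form records a diagnosis

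*SAP*

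**What the plan says.** **Which deaths count.** SAP 5.1 bases outcome events primarily on the outcome CRFs and makes exceptions only for patients who died. One exception covers patients with "fatal AEs and without the death being documented on the outcome CRF; the death will be considered in the outcome analysis", dated at the end of the AE. SAP 6.8 confirms it: "Deaths reported via the vital status or serious adverse event page will also be included".

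**When the cause is missing.** SAP 6.6 treats the cause as missing when it is "neither provided on the patient vital status page nor on the outcome events page". In that case "the death will be considered as 'death of unknown cause' during the data collection". For vascular death, the primary approach is that "multiple imputation will be used to impute the unknown cause of death using the data of patients who died".

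**Which deaths are reviewed.** Where the reason appears only as free text on the vital status page, "a medical review will be done to classify the death into vascular/non-vascular/unknown death", and the result is documented before final database lock. SAP 6.6 also states that the "vital status page is only to be filled for patients who discontinued the study early but allowed for vital status follow up".

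**How the protocol classifies deaths.** Protocol 5.1.2 has three classes: vascular (bleeding included), non-vascular from another specified cause such as malignancy, and unknown, for deaths whose cause is not known.

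**The concern.** The SAP accepts the AE/SAE form as proof that a patient died, but gives it no role in establishing why. If the form is the only record and names a diagnosis, the plan as written sets that diagnosis aside and fills the gap with a statistical draw. The protocol's unknown class does not describe such a death.

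Vascular death is an outcome in its own right. It is also a component of the main composite (with stroke, systemic embolism, MI and life-threatening bleeding) and of the vascular composite (with stroke, systemic embolism and MI). A cancer death imputed as vascular can add an event to all three. A stroke death imputed as non-vascular can remove one.

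**Working it through.** No formula applies: the plan gives no figure on this point and no count of AE-only deaths. The check is to trace such a death through the rules.

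**Step 1: does the death enter the analysis?** Yes, by SAP 5.1 and 6.8.

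**Step 2: can its cause be known?** SAP 6.6 names two pages. By definition, an AE-only death has its cause on neither.

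**Step 3: does the medical review reach it?** No. The review is triggered by free text on the vital status page, and SAP 6.6 limits that page to early discontinuers who allowed vital status follow-up.

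**Step 4: what else could rescue it?** SAP 5.1 has two provisions. An AE that suggests an outcome event without a matching outcome-CRF entry is queried. A major bleed on the bleeding page that is linked to a fatal SAE is counted as a life-threatening bleed.

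**Step 5: results by case.** In every case the death itself is on neither the outcome CRF nor the vital status page, and any query is unresolved.

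| Record | Vascular death | Main composite | Vascular composite |
|---|---|---|---|
| Cancer, SAE form only | imputed | imputed | imputed |
| Stroke, SAE form only | imputed | imputed | imputed |
| Stroke on its outcome page, death on SAE form | imputed | counted as stroke | counted as stroke |
| Major bleed on bleeding page, linked to fatal SAE | imputed | counted as life-threatening bleed | imputed |
| Bleed, SAE form only | imputed | imputed | imputed |

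MI and systemic embolism follow the stroke rows. Vascular death depends on imputation in every row. The composites depend on it only where the table says so.

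**Step 6: is the rule in line with the rest of the plan?**
- For a missing event date, SAP 6.6 first has all of the patient's collected data reviewed and imputes only if that fails. Cause of death has no such step.
- SAP 5.1 already uses SAE outcome and seriousness fields to derive fatal bleeds, so using SAE data for classification is not foreign to the plan.

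**Step 7: would the sensitivity analyses show the effect?**
- SAP 7.6 item (i) sets unknown causes to all vascular, then all non-vascular. Neither uses the recorded diagnosis.
- For the main composite in 1160.136, SAP 7.6 limits the sensitivity analyses to (d) and (f), so (i) is not on the list. SAP 6.6 says only that the two alternatives will be considered.
- SAP 7.6 part 3 names (i) for the vascular composite, but does not say whether the limit for 1160.136 applies there.

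**The case against.** The strongest answer is the query in SAP 5.1. Death is itself a listed outcome event, so a fatal SAE without a death entry is the kind of mismatch that the query is meant to catch. SAP 6.6 adds that investigators must enter all outcome information since the last visit. This stands as a limit on the problem: only deaths unresolved at lock are exposed. It does not remove the problem. A query is not a derivation rule, and the AE-only exception in SAP 5.1 exists for deaths that are still absent from the outcome CRF. The form-status criteria in SAP 6.3 ask for approved or completed forms and do not require queries to be closed.

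Second, the imputation model is unspecified beyond the use of data from patients who died. AE diagnoses could be predictors. That is possible, but nothing requires it, and a recorded cause should be classified before any model is used.

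Third, all-cause death is a separate outcome, and SAP 7.6 item (j) would substitute it for vascular death in the composite. Neither depends on cause. But (j) is optional and is not among the analyses listed for 1160.136.

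Three stronger readings are tempting, and the documents do not support them:
- A reader might infer that a recorded fatal stroke or bleed is lost from both composites. Rows 3 and 4 of the table show otherwise when the event stands on its own page.
- A reader might infer a pull toward no difference. That depends on an imputation model that the SAP does not describe.
- A reader might infer a difference between treatment groups, because SAEs related to the sponsor's drugs are submitted in an expedited manner. Protocol 5.2.2.2 has all SAEs and outcome events collected whatever the drug or causality. Expedited submission concerns transmission to the sponsor, and nothing shows that it produces more AE-only deaths in one group.

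**Conclusion.** The point holds in a limited form. As written, SAP 6.6 labels an AE/SAE-only death unknown and imputes its vascular status even when a diagnosis is recorded, which conflicts with protocol 5.1.2. It applies to deaths that the SAP 5.1 query leaves without an outcome-CRF entry. Vascular death is always affected for these patients. Each composite is affected only where no event that counts toward it stands on its own outcome page.

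The size cannot be calculated. The documents give no number of such deaths and no split by cause or treatment, and the number may be zero. The direction of any bias is likewise undetermined. What is certain is that, for each such death with a recorded diagnosis, the stated rule gives that diagnosis no role in the classification. The conclusion assumes that SAP 6.6 is applied as written and that no separate working document adds the AE/SAE form as a source. The change is worth making before lock because it is cheap and the present rule gives a classification that the protocol does not support.

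**What to change.** In SAP 6.6:
1. Add the fatal AE/SAE form as a third source for cause of death.
2. Extend the existing pre-lock medical review to deaths known only from that form. Classify each as vascular, non-vascular or unknown by protocol 5.1.2, with index treatment hidden from the reviewer, and document the result where the vital-status classifications are already documented.
3. Apply multiple imputation only to deaths still unknown after that review.

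The report should state how many deaths came in by this route and how each was classified.

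The change should stop at cause of death. Counting a stroke, systemic embolism, MI or bleed as a component directly from an SAE term would depart from the SAP's reliance on outcome CRFs, and a reported term need not show that the protocol's event criteria were met.

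The cost is SAP wording and a few more cases in a review already planned. No new data, visits or patients are needed.

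### Outcome events with no recoverable date are imputed to the start of the reporting interval, which puts nearly all first-visit events and some later ones on the index drug, and no sensitivity analysis varies the date

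*SAP*

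**What the plan says.** SAP 6.6 treats missing event dates patient by patient. As a first step, "all collected data for this patient will be reviewed to recover the missing outcome event date". If that yields nothing, there are two cases. For an event documented at the first follow-up visit, "the date of the outcome event will be imputed with the start of the initial treatment regimen episode+1day". An event documented later is dated "with the visit date of the previous follow up visit, otherwise". The same section explains that "investigators have to enter all outcome event information and changes in medication since the last study visit", so an undated event can lie anywhere between the last completed visit and the visit that reports it.

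SAP 6.8 then uses the date twice. For counting: "An event will be counted for the main analysis if it occurs during the initial treatment regimen episode of the antithrombotic therapy selected at baseline". For timing: "The time to event will be calculated as: event date - initial treatment regimen episode start date + 1". Under SAP Table 6.1.2:1 the episode ends at the earliest of permanent stop plus 3 days (6 for VKA), the day before another anticoagulant starts, and the end of study participation. Protocol 6.2.2 sets Phase III visits at 6, 12, 24 and 36 months and collects start and stop dates of antithrombotic treatment.

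**The concern.** Both imputed dates sit at the early end of an interval that is normally 6 or 12 months long. In an as-treated analysis that choice is not neutral. A patient who switched in month 2 and whose undated event is reported at month 6 is counted as an event on the original drug at day 2, although the switch date is on file. The error goes one way: among patients on the index drug at the start of the interval, events after a stop are turned into on-drug events, and never the reverse.

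Timing is affected too. Imputed events stack at day 2 and on visit dates, which adds to early cumulative risk in the Kaplan-Meier estimates.

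None of the sensitivity analyses (a) to (k) in SAP 7.6 varies the imputed event date. For 1160.136 only (d) and (f) are run. By contrast, SAP 6.6 tests unknown cause of death with two opposite imputations.

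**Working it through.** **Inputs.** Visit times are from Protocol 6.2.2. The rate of 25% per year is from Protocol 7.6, where it combines treatment discontinuation and loss to follow-up. The episode, counting and timing rules are from SAP 6.1.2 and 6.8. Assumptions: undated events are uniform within the interval, visits occur at nominal times, none is missed, and the 3- or 6-day washout is ignored.

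**1. Check of the 25% input.** The plan gives no figure on undated events, but its patient-years can be reproduced. With k = −ln(0.75) = 0.2877, patient-years = n(1 − 0.75^T)/k. For 2,500 patients over 2 years this gives 3,801.9 (stated 3,802). For 2,000 over 3 years it gives 4,019.2 (stated 4,019).

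**2. Imputed time for first-visit events.** (start + 1) − start + 1 = 2 days. Every such event falls in the band up to 3 months in SAP 7.6, although the visit reporting it is at 6 months. The only way it can miss the index episode is an episode that ends on day 1.

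**3. Share misattributed, given on drug at interval start.** For an interval of L years the share is 1 − (1 − e^(−kL))/(kL).
- L = 0.5: 1 − 0.1340/0.1438 = 6.9%.
- L = 1: 1 − 0.25/0.2877 = 13.1%.

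The 25% includes loss to follow-up, and a lost patient has no later visit at which to report an event. These are therefore upper bounds at nominal visit spacing. If half the rate were treatment stop (12.5% per year, an assumption), the shares are 3.3% and 6.4%. A missed visit lengthens the interval and raises the bound: for L = 2 it is 1 − 0.4375/0.5754 = 24.0%.

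**4. All undated events, including patients already off drug (25% per year).**

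| Reported at | Placed on drug by the rule | Truly on drug | Excess, points |
|---|---|---|---|
| 6 months | 100% | 93.1% | 6.9 |
| 12 months | 86.6% | 80.7% | 5.9 |
| 24 months | 75.0% | 65.2% | 9.8 |
| 36 months | 56.25% | 48.9% | 7.4 |

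The remaining 13.4%, 25.0% and 43.75% at the later visits had ended the episode by the previous visit and are not counted. Weighting the intervals by length over 3 years, the rule places 74.9% on drug against 67.0% truly on drug, an excess of about 8 points. At 12.5% per year it is 86.9% against 82.4%, about 4.5 points.

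**5. Scale.** The undated share is not given; take 1% to 5%. Then 1% × 6.9% = 0.07% and 5% × 13.1% = 0.66%, or about 0.1% to 0.7% of events. As an illustration, 4,019 patient-years at the protocol's 1 to 3 events per 100 (its range for stroke/SEE and major bleeding) give 40 to 121 events. Of these, 0.4 to 6 would be undated, and at 13.1% fewer than one would be misattributed (6 × 0.131 = 0.8).

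**The case against.** The strongest reply is that this is a last-resort rule with safeguards. All the patient's data are reviewed first, the proportion with partial dates is evaluated, and each decision is minuted. The intention-to-treat analyses do not censor at discontinuation, so the on- or off-drug question disappears there, and analysis (d) is kept for 1160.136. All of this stands, and it limits the size of the problem. It does not remove it: minutes and proportions record the issue without bounding it, and the intention-to-treat analysis keeps the artificial date.

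A reader might infer that the rule always places undated events on the index drug. The documents do not support that. A later-visit event in a patient whose episode had ended by the previous visit receives a date after the episode and is excluded under SAP 6.8.

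A reader might also infer a bias between arms. If discontinuation were 30% against 20% per year, the 12-month shares would be 15.9% and 10.4%. Neither document gives arm-specific rates, so the contrast is hypothetical; even then, at 5% undated, it is (15.9% − 10.4%) × 5%, about 0.3% of events.

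Finally, a fixed midpoint would not cure the clustering. It would stack events at about months 3, 9, 18 and 30, and three of these are boundaries of the Kaplan-Meier bands in SAP 7.6.

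**Conclusion.** The point holds in a limited form. The rule is one-directional for patients on drug at interval start. It gives every undated first-visit event a time of 2 days, and no planned analysis tests it. Misattribution in that group is at most about 7% to 13% of undated events at nominal visit spacing, and roughly half that if only half of the 25% is treatment stop. The effect on the main result depends on an undated share that the documents do not state. At an assumed 1% to 5% it is about 0.1% to 0.7% of events at most, which is unlikely to change a conclusion. The case for changing it is that the direction of the error is known in advance and the remedy costs little, not that the main comparison is in danger.

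**What to change.** In SAP 6.6, replace the two start-of-interval dates with a uniform random draw between the last contact without the event and the visit that reports it, restricted to any known month or year. Ideally make the draw inside the multiple imputation already planned for covariates and cause of death. Tables and curves not combined over imputations can use one draw with a stated seed. Then apply the SAP 6.1.2 episode rule to the drawn date, using the recorded stop and switch dates.

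Add earliest-date and latest-date imputation to the sensitivity analyses in SAP 7.6 as bounds, and include 1160.136, which is otherwise limited to (d) and (f). Report the number of undated events by treatment group and reporting visit.

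The cost is a few sentences of SAP text and minor programming, with no new data. A few events may move off the index drug, and for a single patient the draw can be wrong in either direction; the two bounds show how much that matters.
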